### 5.3 Schematic diagram

A schematic diagram is provided in Figure 5-1.

Figure 5-1: Study design

bid=twice daily; d=day; Echo=echocardiogram; EDV=Early Discontinuation Visit; IMP=investigational medicinal product; m=months; OLE=open-label extension; PSL=padsevonil; Stab=Stabilization Period; TC=telephone contact; V=Visit; Wk=Week

## **5.4 Rationale for study design and selection of dose**

### **5.4.1 Choice of study design and endpoints**

The target indication for PSL is as adjunctive therapy in the treatment of focal-onset seizures in adult patients with drug-resistant epilepsy. The key inclusion criteria are aimed at selecting a sample of subjects from this target population. The criterion for drug resistance or failure to achieve control of seizures, with  $\geq 4$  tolerated and appropriately chosen past or current AEDs, is based on observations that when patients with drug-resistant epilepsy have not been able to control their seizures despite treatment with 4 or more AED regimens, the likelihood of achieving complete seizure control with another AED regimen is further reduced to 1% to 4% (Schiller and Najjar, 2008; Mohanraj and Brodie, 2006). Subjects also will be required to have on average at least 4 spontaneous and observable focal-onset seizures (IA1, IB, or IC) per 28 days during each 4-week interval of the 8 weeks prior to the Screening Visit and during the 4-week Baseline Period. This minimum seizure frequency was selected to provide assurance that a meaningful change in percent reduction in seizure frequency over 28 days and 50%, 75%, and 90% responder rates could be demonstrated during the 12-week Maintenance Period.

The key exclusion criteria are intended to further ensure correct diagnosis of epilepsy, that the disease is relatively stable, that there are no drugs/treatments which could confound analyses or present a safety issue as a result of DDI or efficacy against seizures, that there is no evidence of previous safety issues with other drugs that share PSL's mechanisms of action, and to mitigate risks or potential risks to subjects from this target population.

UCB regards the 12-week duration for the Maintenance Period as adequate to distinguish long-term from short-term efficacy. Moreover, 12 weeks is consistent with registration studies for recently approved AEDs as adjunctive therapy for focal-onset seizures (Moseley et al, 2016; Chung et al, 2010b; Elger et al, 2009) and conforms to the guidance documents by the FDA, Guidance for Industry, 1981 and EMA (CHMP/EWP/566/98 Rev.2/Corr, 2010). Given the increased risk of SUDEP in patients with uncontrolled seizures (Jehi, 2016) and in those randomized to placebo in clinical studies (Ryvlin et al, 2011), UCB considers that requiring patients to remain on placebo longer or for all enrolled patients to exclude dose adjustments is not acceptable. Because of the increased incidence of SUDEP, subjects should be monitored closely and, depending on the Investigator's judgment, withdrawn from the study in the event of seizure worsening, particularly subjects experiencing an increase in secondarily generalized seizures. Additionally, a 3-week Titration Period, 1-week Stabilization Period, and 12-week Maintenance Period have been assessed as adequate to evaluate the potential for the development of tolerance to BZDs associated with a reduction in long-term efficacy for both clobazam and brivaracetam.

Similarly, UCB proposes to perform an examination of the reduction in seizure frequency from Baseline to assess whether there is any evidence of a notable change in treatment effect during the course of the 16-week Treatment Period for EP0092.

### **5.4.2 Rationale for dose selection**

Nonclinical efficacy data indicate that receptor occupancy at both the SV2 and GABA-A molecular targets contribute to the mode of action of PSL (Wood et al, 2017). In addition, a comprehensive analysis of data from 2 human PET studies (UP0036 and N01383, addressing both SV2A and GABA-A occupancy, respectively), together with population PK modelling of

patient PK data from EP0069, has allowed exploration of the occupancy levels at each of the 2 targets with simulated dosing regimens (UCB internal data). Dosing regimens of 200mg bid and 400mg bid are expected to result in high (>90%) and sustained SV2A occupancy, and quantifiable and relatively low GABA-A occupancy (ie, approximately 6% and 13% for 200mg bid and 400mg bid, respectively). These levels of target engagement are predicted by preclinical data to be required for efficacy in the drug-resistant population, and efficacy was demonstrated at 400mg bid in the clinical study, EP0069. At 100mg bid, the simulations referred to above predict sustained SV2A occupancy to be >90% in 75% of the population, and GABA-A occupancy below the limit of quantification for the flumazenil human PET model. The receptor occupancy data indicate that doses of 100, 200, and 400mg bid will engage the presynaptic SV2 proteins (for all 3 doses) and the postsynaptic GABA-A receptors (for at least the 2 higher doses). Thus, the doses of 100mg bid, 200mg bid, and 400mg bid are predicted to span the dose range which will be efficacious in the drug-resistant patient population that will enroll in EP0092 based on quantitative evidence of target coverage and systemic exposure.

Subjects completing the Maintenance Period in EP0092 will be offered the option to enter the OLE study, EP0093, with open-label treatment with PSL. This will be achieved through a Conversion Period to ensure blinding of the parent study. All subjects who choose to transition to EP0093 will enter the study after the 3-week Conversion Period at an intermediate dose of PSL 200mg bid before further individual dose adjustment can be made. This dose level was selected considering the benefit/risk balance and is based on clinical pharmacology and PET data in healthy human subjects suggesting that it will provide full occupancy at the SV2A binding site while maintaining some minimal binding to the GABA-A binding site. For subjects previously on placebo in EP0092, a full SV2A occupancy is desirable to obtain a meaningful anticonvulsive effect while minimal BZD binding will result in fewer GABA-related CNS AEs. On the other hand, for subjects exposed to high doses of PSL during the EP0092 Maintenance Period (400mg bid), the target transition dose of 200mg bid will likely maintain the full SV2A-related effect while not entirely eliminating GABA-binding related effects.

## **6 SELECTION AND WITHDRAWAL OF SUBJECTS**

### **6.1 Inclusion criteria**

To be eligible to participate in this study, all of the following criteria must be met:

#### **General**

1. An Institutional Review Board (IRB)/Independent Ethics Committee (IEC) approved written ICF is signed and dated by the subject or by the parent(s) or legal representative, where applicable. The ICF or a specific Assent form, where required, will be signed and dated according to country-specific regulations.
2. Subject/legal representative is considered reliable and capable of adhering to the protocol (eg, able to understand and complete diaries), visit schedule, and medication intake according to the judgment of the Investigator.
3. Subject is an adult (18 years of age or more).
4. Subject is of normal weight of at least 40kg (for males and females).

## Epilepsy

5. Subject fulfills diagnostic criteria for epilepsy and has observable focal-onset (IA1, IB, and IC) seizures for at least 3 years at the time of enrollment (according to the ILAE Classification of Epileptic Seizures, 1981):
  - Epileptic seizures have been documented using video-EEG recordings or ictal-EEG ( $\pm$ simultaneous video) in the past (description or report is available). The Investigator must consult with the UCB Study Physician or representative for confirmation of eligibility as per instructions in the Study Manual.

If no video-EEG report is available and, in the opinion of the Investigator, epileptic seizures are definite (ie, eye-witnessed seizure report, home video documentation of habitual events, or other proof), the Investigator must consult with the UCB Study Physician or representative for a case review.
  - A brain magnetic resonance imaging (MRI) is to be performed before randomization, if no such scan was performed in the last 10 years, and a report is not available. If a scan was performed within the last 10 years but the clinical condition of the subject was progressive since the last scan, a new scan should be obtained. If MRI is contraindicated, a head computed tomography scan within the last 3 years before randomization will suffice.
6. Subject has on average  $\geq 4$  spontaneous and observable focal-onset seizures per 28 days (based on Investigator assessment of subject report) with at least 1 seizure during each 4-week interval of the 8 weeks prior to the Screening Visit. Additionally, subject must experience  $\geq 4$  spontaneous and observable focal-onset seizures per 28 days (based on Investigator assessment of subject report) during the 4-week Baseline Period.
7. Subject has failed to achieve seizure control with  $\geq 4$  tolerated and appropriately chosen prior AEDs, including past and ongoing treatments that were individually optimized for adequate dose and duration. Prior discontinued AED treatment would need to be assessed by the Investigator considering the patient medical records and patient and/or caregiver interview. "Prior AED" is defined as all past and ongoing AED treatments with a start date before the Screening Visit (Visit 1).

## Concomitant epilepsy treatment

8. Subject is currently treated with an individually optimized and stable dose of at least 1 and up to 3 AEDs for the 8 weeks prior to the Screening Visit (Visit 1) with or without additional concurrent vagus nerve stimulation (VNS) or other neurostimulation treatments. The latter will not be counted as AEDs for the purpose of eligibility.

## Laboratory parameters

9. Subject has clinical laboratory test results within the reference ranges of the laboratory or isolated test results that are outside the specified ranges and deemed as not clinically significant by the Investigator, eg, mild and moderate renal impairment.

## Birth control

10. Female subjects of child bearing potential must have a negative serum pregnancy test at the Screening Visit (Visit 1), which is confirmed to be negative by urine testing prior to the first dose of IMP at Day 1 (Visit 2) and prior to further dispensing at each study visit thereafter. Subjects will be withdrawn from the study as soon as pregnancy is known.

Female subjects will use an efficient form of contraception for the duration of the study for a period of 3 months after their last intake of IMP. Hormonal contraception may be susceptible to an interaction with the IMP, which may reduce the efficacy of the contraception method. The potential for reduced efficacy of any hormonal contraception method requires that a barrier method (preferably a male condom) also be used.

Birth control methods considered as an efficient form of contraception:

- Combined (estrogen- and progesterone-containing) hormonal contraception (oral, implant, injectable) associated with inhibition of ovulation (which must be stable for at least 1 full month prior to Screening [Visit 1], and should remain stable during the study) in combination with a barrier method (preferably a condom).
- Progesterone-only hormonal contraceptives (oral, implant, injectable) associated with inhibition of ovulation (which must be stable for at least 1 full month prior to Screening [Visit 1], and should remain stable during the study) in combination with a barrier method (preferably a condom)
- Progesterone-releasing intrauterine systems or the TCU 380A intrauterine device in combination with a barrier method (preferably a condom)
- Progestogen-only oral hormonal contraception, where inhibition of ovulation is not the primary mode of action, in combination with a barrier method (preferably a male condom)
- Male or female condom with spermicide (ie, double-barrier)
- Cap, diaphragm, or sponge with spermicide (ie, double-barrier)
- Bilateral tubal ligation
- Vasectomized partner (provided sole partner, and partner has medical proof of surgical success)
- True heterosexual sexual abstinence is an acceptable form of contraception when this is in line with the preferred and usual lifestyle of the person. Periodic abstinence (eg, calendar, ovulation, symptothermal, post-ovulation methods), declaration of abstinence for the duration of the study, and withdrawal are not acceptable methods of contraception.
- Women not agreeing to use birth control must be abstinent (as described in the preceding bullet) or be of nonchildbearing potential, defined as being postmenopausal (for at least 2 years before the Screening Visit [Visit 1]), verified by serum follicle stimulating hormone level >40mIU/mL at the Screening Visit (Visit 1), or permanently sterilized (eg, bilateral tubal occlusion, hysterectomy, bilateral salpingectomy), or congenitally sterile.

- Both male and female subjects must use the above-mentioned contraception during the study.
- To ensure a proper birth control, females who use hormonal contraception should use an efficient barrier contraceptive in the 3 months after their last intake of IMP.

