**Table 5-1: Schedule of assessments**

Visit	BL Period (4 weeks)	Treatment Period (16 weeks)										SFU Period (30 days after IMP intake)	Unsch Visit b	
		Titration Period (3 weeks)			Stab Period (1 week)	Maintenance Period (12 weeks)				Taper/Conversion Period (3 to 4 weeks) a				
		V2 BL	TC	V3	TC	V4	V5	V6	V7 (EDV/EOT)	TC	V8 (Conversion)			V8 (Taper)
Wk -4	D 1	Wk 1	Wk 2	Wk 3	Wk 4	Wk 8	Wk 12	Wk 16		Wk 19	Wk 20	Wk 23		
Day Number	-28	1	7	14	21	28	56	84	112		133	140	161	
Visit Window (days)		±3	±3	±3	±3	±7	±7	±7	±7		±7		±7	
Assessments														
Written informed consent	X													
Call IRT to obtain subject number and dispensation of Subject Trial Card	X													
Demographic data	X													
Habits and lifestyle	X													
Verification of inclusion/exclusion criteria	X	X												
Verification of withdrawal criteria		X	X	X		X	X	X	X					
General medical/procedures history	X													
Epilepsy history including etiology, diagnosis, surgery, and seizure history	X													
Documentation of MRI (within 10 years)	X													

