- m AED samples will ideally be taken immediately prior to dose of concomitant medication on each occasion. If this is not possible, then the sample may be taken at any time after dose and the timing of sample in relation to dose should be kept the same ( $\pm 1$  hour) on each occasion for each subject. Therefore, the timing of visits for each subject when AED samples are collected should be scheduled approximately at the same time whenever possible. Assay of parent PSL and metabolites may be included in the AED panel of tests at Visits 6 and 7.
- n On Visits 6 and 7, unless the concomitant AED sample is within  $\pm 5$  minutes of a scheduled MITRA® sample for PSL assay, a separate, additional MITRA sample will be taken at same time as the concomitant AED blood sample.
- o Subjects are requested to provide blood samples for measurement of PSL PK whenever possible. On Visits 3, 5, and 6, site personnel should obtain blood samples, via MITRA microsampling, for measurement of random PSL levels at any time between IMP intakes and record accurately the time of last IMP intake and the time of sample collection. On Visits 4 and 7, blood samples, via MITRA microsampling, for measurement of sparse PK profiles will be collected as follows: immediately before IMP intake (maximum 15 minute before intake) and then 3 times after (between 30 minutes and 3 hours after IMP intake), taken at least 30 minutes apart. All samples may be taken either at home or in the site or partly at home and partly at the site.
- p For all female subjects, serum pregnancy test at Visits 1 and 7 (in case the subject enters into the OLE study) and where applicable. Urine pregnancy test will be used at other visits for female subjects of childbearing potential.
- q Seizure counts are collected on the subject's daily record card on a daily basis.
- r At each visit following an IMP dispensation, IMP should be presented to check for compliance.
- s Study termination will occur at Visit 8 only for subjects enrolling in OLE study, EP0093. The SFU Visit will be performed only for subjects who do not enter the OLE study, EP0093.

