10. For subjects developing psychiatric/mood/behavioral signs or disturbances (see examples in list below) that are clinically concerning or that worsen over time, the subject should be referred immediately to a mental healthcare professional and must be withdrawn from the study.
  - Auditory or visual hallucinations
  - Delusions/paranoia/grandeur
  - Disorganized thought process
  - Agitation/aggression/apathy
  - Dysphoria/depression/mood lability/euphoria
  - Disinhibition
  - Cognitive changes/memory impairment/delirium
  - Aberrant motor behavior

11. Subject is suspected of having a serious multiorgan hypersensitivity reaction. Serious suspected multiorgan hypersensitivity cases may be identified and reported to the Sponsor by the Investigator using the following algorithm:
- An AE or laboratory value (as defined below) suggestive of internal organ involvement including but not limited to hepatitis, nephritis, pneumonitis, carditis, colitis, encephalitis, pancreatitis, myositis, arthritis, or hematologic system involvement, combined with at least 1 of the following: fever, rash, lymphadenopathy, or eosinophilia
  - Treatment-emergent abnormal laboratory value criteria suggestive of internal organ involvement or eosinophilia:
    - Eosinophils percentage  $\geq 10\%$
    - Eosinophils absolute  $\geq 0.5\text{G/L}$
    - Neutrophils absolute  $< 1.5\text{G/L}$
    - Platelets absolute  $\leq 100\text{G/L}$
12. There is confirmation of a pregnancy during the study, as evidenced by a positive pregnancy test.

Investigators should attempt to obtain information on subjects in the case of withdrawal or discontinuation. For subjects considered as lost to follow up, the Investigator should make an effort (at least 1 phone call and 1 written message to the subject), and document his/her effort (date and summary of the phone call and copy of the written message in the source documents), to complete the final evaluation. All results of these evaluations and observations, together with a narrative description of the reason(s) for removing the subject, must be recorded in the source documents. The eCRF must document the primary reason for withdrawal or discontinuation.

Investigators should contact the Medical Monitor, whenever possible, to discuss the withdrawal of a subject in advance.

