## **8.2 Treatment Period (16 weeks)**

### **8.2.1 Titration Period (3 weeks)**

#### **8.2.1.1 Visit 2, Baseline (Day 1, 4 weeks after Visit 1, $\pm 3$ days)**

The following procedures will be performed:

- Verify Inclusion and Exclusion criteria (including results of laboratory parameters, ECG, echocardiogram, and MRI obtained since Visit 1). In the event 1 of these results is not available, the visit may be delayed by 1 week.
- Verify withdrawal criteria
- Randomize subjects using IRT
- Obtain C-SSRS data since the last visit
- Obtain HADS data
- Obtain SSG data

- Obtain QOLIE-31-P data
- Measure vital signs (pulse rate, respiratory rate, SBP, and DBP), in supine position after 5 minutes of rest
- Measure body weight
- Perform brief physical examination (refer to Section 11.7.4 for details)
- Perform brief neurological examination (refer to Section 11.7.5 for details)
- Perform Psychiatric and Mental Status assessment
- Obtain 12-lead ECG
- Collect blood and urine samples for clinical laboratory analyses
- Collect blood sample for concomitant AED assay
- Perform urine pregnancy test (female subjects of childbearing potential only)
- Seizure evaluation (count and type) from subject's daily record card
- Record concomitant medications (AEDs and non-AEDs) and procedures
- Record AEs
- Record health-related outcomes and HRU (refer to Section 9.5 for details), with the exception of socio-professional status
- Dispense IMP using IRT

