### **8.2.3.3 Visit 7 (Week 16 $\pm$ 7 days for EOT or earlier for EDV)**

The following procedures will be performed:

- Verify withdrawal criteria

- Obtain C-SSRS data since the last visit
- Obtain HADS data
- Obtain SSG data
- Obtain QOLIE-31-P data
- Obtain CIWA-B data (only for subjects tapering)
- Measure vital signs (pulse rate, respiratory rate, SBP, and DBP), in supine position after 5 minutes of rest
- Measure body weight
- Perform full physical examination (refer to Section 11.7.4 for details)
- Perform full neurological examination (refer to Section 11.7.5 for details)
- Perform Psychiatric and Mental Status assessment
- Obtain 12-lead ECG
- Collect blood and urine samples for clinical laboratory analyses
- Collect blood sample for concomitant AED assay including an additional MITRA sample if the AED sample is not within  $\pm 5$  minutes of one of the scheduled PSL PK samples
- Obtain blood samples, via MITRA microsampling, immediately before final IMP intake from the previously dispensed Maintenance kit (maximum 15 minutes before IMP intake) and then 3 times after (between 30 minutes and 3 hours after IMP intake) taken at least 30 minutes apart (sparse PK profiles)
- Perform urine pregnancy test (for female subjects of childbearing potential discontinuing the study only) or serum pregnancy test (for female subjects continuing into the OLE study)
- Seizure evaluation (count and type) from subject's daily record card
- Record concomitant medication (AEDs and non-AEDs) and procedures
- Record AEs
- Record health-related outcomes and HRU (refer to Section 9.5 for details)
- Dispense IMP using IRT
- Check IMP accountability

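### At Visit 7, women entering the OLE get a serum pregnancy test in place of the urine test that criterion 10 requires before dispensing, and release of the Conversion supply is not tied to its result

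*Protocol*

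**What the plan says.** Criterion 10 in protocol 6.1 has two parts. A woman of childbearing potential needs a negative serum test at screening, and this must then be confirmed "negative by urine testing prior to the first dose of IMP at Day 1 (Visit 2) and prior to further dispensing at each study visit" from then on. The later part is a condition on dispensing, and the test it names is urine.

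For Visit 7, section 8.2.3.3 lists a "urine pregnancy test (for female subjects of childbearing potential discontinuing the study only) or serum pregnancy test (for female subjects continuing into the OLE study"). Further down, the same list has "Dispense IMP using IRT", with nothing linking the two items. Footnote p to Table 5-1 is in line with this: it calls for a "serum pregnancy test at Visits 1 and 7 (in case the subject enters into the OLE study") and places urine testing at other visits. The SAP's copy of the schedule (Table 2-1) repeats that footnote.

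Section 11.6 differs slightly. It assigns the serum test at Visits 1 and 7 to women of childbearing potential generally, without limiting Visit 7 to OLE entrants. The section opens by sending laboratory assessments to a central laboratory.

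**The concern.** Criterion 10 exists so that study drug is not handed to a woman who is already pregnant. At Visit 7 the test it names is not the one listed for women going on to the OLE, and no sentence carries its condition over to the serum result.

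The visit also matters more than an ordinary resupply. Under section 7.2.3 and Table 7-4, subjects on placebo move to active padsevonil during Conversion, so for a woman on placebo this is the first release of active drug. Women on a padsevonil arm have by then had about 16 weeks of exposure, and for them the visit resembles the earlier ones. What is at stake is avoidable early exposure in a small group, and a written plan that a site cannot follow on both counts. No efficacy estimate, error rate or power figure is involved.

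**Working it through.** There is no planned figure to reproduce. The check sets the texts side by side for a woman of childbearing potential who enters the OLE.

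| Visit | Nominal day | Pregnancy test listed | IMP dispensed |
|---|---|---|---|
| 2 | 1 | urine | yes |
| 3 | 14 | urine | yes |
| 4 | 28 | urine | yes |
| 5 | 56 | urine | yes |
| 6 | 84 | urine | yes |
| 7 | 112 | serum | yes (Conversion) |
| 8 (Conversion) | 133 | urine | no |

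The sources are Table 5-1 with footnote p, and sections 8.2.1 to 8.3.2. Urine is listed at 5 of the 6 dispensing visits (Visits 2 to 6); the exception is Visit 7.

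**Does anything else at Visit 7 hold back dispensing until the result is known?**

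1. *Eligibility check.* Criterion 10 sits among the inclusion criteria. The Table 5-1 row "Verification of inclusion/exclusion criteria" is marked at Visits 1 and 2 only.
2. *Withdrawal check.* Section 8.2.3.3 does include "Verify withdrawal criteria". The relevant criterion in section 6.3 is "There is confirmation of a pregnancy during the study, as evidenced by a positive pregnancy test". It acts on a positive test, so a pending result triggers nothing.
3. *Delay rule.* Section 8.2.1.1 has one for Visit 2, covering laboratory, ECG, echocardiogram and MRI results: "In the event 1 of these results is not available, the visit may be delayed by 1 week". Visit 7 has no counterpart.
4. *Conversion and OLE text.* Sections 5.1, 7.2.3 and 8.6 do not mention a pregnancy result.

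**Could the serum result be pending?** Criterion 10 expects a urine result before dosing at Visit 2, where the test is done and drug dispensed at one visit, so that test must be readable within the visit. For serum there is no such indication. The test is described in section 11.6, which uses a central laboratory. Table 11-2 does not list it, and no turnaround is given. Delay is plausible; the documents do not establish it.

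**How soon is the next scheduled test?** Visit 7 to Visit 8 is 133 − 112 = 21 days. The preceding intervals are 56 − 28 = 28, 84 − 56 = 28 and 112 − 84 = 28 days. These are nominal days with a ±7-day window.

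**What share would come from placebo?** Randomization is 1:1:1:1. If OLE uptake is equal across arms (an assumption), it is 1/4.

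**The case against.** The strongest reply is that criterion 10 still applies. It speaks of every later visit at which drug is dispensed, and Visit 7 is one. Read literally, it demands a urine test there; read sensibly, it covers the serum test listed in its place. On either reading, dispensing on a pending result does not comply. The lists for Visits 3 to 6 also show a test and a dispensing step with no link between them, so pointing out that inclusion criteria are verified only at Visits 1 and 2 would prove too much if it were the whole argument.

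Much of this stands. It would be wrong to say that no rule applies at Visit 7. But if criterion 10 binds, it conflicts with 8.2.3.3, which reserves urine for women who are discontinuing. At Visits 3 to 6 the listed test is the one criterion 10 names, so the condition carries over directly; at Visit 7 a site has to infer it.

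The second reply is that the harm is conjectural. The Laboratory Manual, the interactive response technology (IRT) specification and the OLE protocol are not part of these documents and may close the gap. Safeguards are already in place: the urine test at Visit 6, required contraception (6.1), an interim test if pregnancy is suspected (11.6), withdrawal on a positive test (6.3), and stopping or down-titration (11.2). This stands as well, and it is why the point is minor.

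A reader might infer that women will receive the Conversion supply before their result is known, or might try to put a dose in mg on the exposure. The documents support neither. The delay is not stated and may be zero. Table 7-4 lets steps vary by ±3 days per week. The start of Conversion on the day after Visit 7 comes from SAP Table 3-1, which classifies data and does not instruct dosing. A Conversion dose on the evening of Visit 7 is not excluded.

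**Conclusion.** The inconsistency holds. Criterion 10 requires a negative urine test before dispensing, 8.2.3.3 and footnote p give OLE entrants serum instead at Visit 7, and dispensing there is not tied to the serum result. A result still pending at dispensing is plausible and not shown.

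The size is small: one of six dispensing visits, for women of childbearing potential entering the OLE, whose number is not given. The main interest is in those on placebo, about a quarter under the equal-uptake assumption. No amount of exposure should be quoted. The SAP (3.9) records early termination of the study, which limits the practical benefit here but does not reconcile the texts. The conclusion rests on the protocol and SAP alone; a rule in a manual that is not available could close the gap in practice.

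The mismatch with 11.6 is separate and editorial. It concerns which test women who are discontinuing receive at Visit 7, and has no bearing on the Conversion supply.

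**What to change.** Preferred: in 8.2.3.3, list the urine test used at Visits 2 to 6 for all women of childbearing potential at Visit 7, require a negative result before IMP is dispensed, and keep the serum test for OLE entrants. The cost is one extra urine test per woman of childbearing potential entering the OLE.

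Alternative: reword criterion 10 to accept urine or serum, provided a negative result is available before dispensing, and repeat that condition in 8.2.3.3, where the site will see it on the day. The cost is a possible short wait for the serum result before the Conversion supply is released.

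With either option, align footnote p of Table 5-1 and section 11.6 with 8.2.3.3, and carry the change into the SAP's copy of the schedule. These are wording changes only.
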